1.6 Potential Benefit

The ADX-102-AC-011 clinical trial will evaluate reproxalap in an EEC setting in allergic conjunctivitis patients. No direct benefits are expected from participating in the clinical trial.

Safety of the clinical dosing regimen in this trial is supported by a large number of pre-clinical and clinical, ocular and systemic, and toxicology and pharmacokinetic studies in which no serious safety concerns were noted.

1.7 Rationale for Dose Selection

Ophthalmic dosing is the optimal route of administration for ocular allergy treatments. The dosage and dosage regimen were selected based on nonclinical and clinical studies described in [Section 1.3](#).

2 CLINICAL TRIAL OBJECTIVE AND ENDPOINTS

2.1 Exploratory Objectives

The exploratory objectives of the clinical trial are:

- To evaluate the feasibility of using the EEC clinical trial design to assess the activity of Reproxalap Ophthalmic Solutions (0.25% and 0.5%) in an allergic conjunctivitis population.
- To assess safety, tolerability, and pharmacodynamic activity of Reproxalap Ophthalmic Solutions (0.25% and 0.5%) compared to Vehicle Ophthalmic Solution in the treatment of

seasonal allergic conjunctivitis in subjects allergic to ragweed using the EEC with exposure to airborne ragweed pollen.

2.2 Clinical Trial Assessments and Endpoints

The clinical trial is exploratory in nature to the safety, tolerability, and pharmacodynamic activity of Reproxalap Ophthalmic Solutions (0.25% and 0.5%) compared to Vehicle Ophthalmic Solution in subjects with allergic conjunctivitis in an EEC model. There are no primary endpoints and no formal statistical hypotheses.

The assessments used in this trial include ocular itching self-assessed by each subject using two scales, a Visual Analog Scale (VAS) and a 9-point scale.

VAS is measured on a 0-100 mm continuous scale where 0 is considered no itching and 100 is considered maximum itch.

[figure not shown]
[figure not shown]

Figure 3. Photographic Ocular Redness

2.3 Safety Endpoints

Safety assessments will include Snellen visual acuity (VA), slit lamp examination (SLE) and non-contact intraocular pressure tonometry (NCT) as detailed in [Table 1](#). Dilated fundus examination at screening Visit 1 and at Visit 5 and undilated fundus examination will be performed at Visits 2, 3 and 4. Adverse event (AEs; reported, elicited and observed) assessments will be performed at Visit 2 through Visit 5.

2.4 Exploratory Efficacy Endpoints

The following endpoints will be derived for each treatment visit and will be used to assess the activity of Reproxalap Ophthalmic Solutions.

- AUC 0-212 mins for Itching on VAS scale
- AUC 0-212 mins for Itching on 9 points scale
- AUC 0-210 mins for Conjunctival Redness on 9 points scale
- AUC 0-212 mins for Tearing on 4 points scale
- AUC 0-212 mins for TOSS
- AUC 0-92 mins for Itching on VAS scale
- AUC 92-212 mins for Itching on VAS scale
- AUC 0-32 mins for Itching assessed by VAS Scale
- AUC 32-72 mins for Itching assessed by VAS Scale

All 0 time-point measurements will be pre-EEC entry/ baseline values. All the time-points are approximate values.

2.5 Additional Exploratory Analyses

In addition, change from baseline (CFB) for each treatment and each post-EEC time-points may be derived and used as exploratory efficacy endpoint and used to evaluate the efficacy of Reproxalap Ophthalmic Solutions (0.25% and 0.5%). Other exploratory analyses may be added post-hoc.

3 INVESTIGATIONAL PLAN

3.1 Overall Clinical Trial Design and Plan

[figure not shown]
The double-masked, vehicle-controlled, randomized, three-way crossover clinical trial allows for the testing of two concentrations of Reproxalap Ophthalmic Solution (0.25% and 0.5%) versus Vehicle Ophthalmic Solution in subjects with ragweed-induced allergic conjunctivitis in the EEC.

The clinical trial consists of five visits to the clinic (one Medical Screening visit, one Screening EEC visit, and three EEC treatment visits). The four EEC sessions (one EEC screening and three EEC treatment sessions) will be separated by an approximate two-week washout period to ensure adequate elimination of responses caused by allergen exposure in the EEC and allow the recuperation of mast cells, please refer to Figure 4

The EEC clinical research facility is a room designed with the capacity and control mechanisms to expose participants to airborne ragweed pollen grains and maintains target temperature and relative humidity throughout.

The use of the controlled EEC allergen exposure has been validated to provide spatial and temporal airborne allergen uniformity and to mimic the natural exposure on a peak allergen day.

Figure 4. Clinical Trial Design

At the Medical Screening Visit (Visit 1), subjects will undergo the informed consent process, and information about demographics, baseline characteristics, medical history, social history, physical examination will be performed and concomitant medication will be collected. Vital signs and samples for standard clinical safety laboratory tests will be obtained. A urine pregnancy test will be administered to women of childbearing potential (WOCBP).

Subjects will undergo ophthalmic examinations (Snellen VA, SLE, NCT, and a dilated fundus examination) to ensure initial eligibility criteria are met. A skin prick test for a panel of test allergens will be conducted; results must be positive (i.e., a wheal that is 3 mm greater than the negative control) for at least one test allergen and must include ragweed in order to proceed to Visit 2.

At all EEC sessions, assessments of ophthalmic evaluations will be collected [REDACTED]. For subject-reported symptoms of ocular itching, a standard 9 point (i.e., 0-4 with 0.5 unit increments) and a standard VAS scale (0-100 mm) will be employed and subject reported tearing assessed by a 4-point (0-3) scale will be employed. For staff-assessed grading of conjunctival redness, a standard 9-point (i.e., 0-4 with 0.5 unit increments) will be employed. [REDACTED]

At the EEC Screening Visit (Visit 2), qualified site staff will update concomitant medications and collect AEs, as applicable and perform tests for vital signs. A urine pregnancy test will be administered to WOCBP. Fundus exam, Snellen VA, SLE, subject rating of symptoms, and staff grading of conjunctival redness will be performed to ensure the anterior segment of the eye is healthy. [REDACTED]

Pre-EEC entry (Baseline):

- 1) Subject assessment for ocular itching and tearing will be recorded [REDACTED]
[REDACTED], and
- 2) Staff-assessed conjunctival redness will be recorded [REDACTED]
[REDACTED].

Post-EEC entry:

- 1) Subject assessment for ocular itching and tearing will occur [REDACTED]
- 2) Staff-assessed conjunctival redness will be recorded [REDACTED]
[REDACTED]

Please refer to [Table 2](#), [Table 3](#), [Table 4](#) and [Table 5](#) for schedule of staff and subject assessment time-points.

At Randomization/Treatment EEC Session One (Visit 3), qualified site staff will update concomitant medications, collect AEs, as applicable and collect vital signs. A urine pregnancy test will be administered to WOCBP. Ophthalmic evaluations will be conducted (Fundus exam, Snellen VA, NCT SLE, subject rating of symptoms, and staff grading of conjunctival redness). [REDACTED]

Subjects will be randomized to receive a first dose of either Reproxalap Ophthalmic Solution (0.25%) (Treatment A), Reproxalap Ophthalmic Solution (0.5%) (Treatment B), or Vehicle Ophthalmic Solution (Treatment C). Qualified site staff will instill one drop of the randomized

treatment into each eye at approximately five minutes prior to entry to the EEC after all the pre-EEC assessments are done.

Pre-EEC entry (Baseline):

- 1) Subject assessment for ocular itching and tearing will be recorded [REDACTED]
[REDACTED] and
- 2) staff-assessed conjunctival redness will be recorded [REDACTED]
[REDACTED].

Post-EEC entry:

- 1) Subject assessment for ocular itching and tearing will occur [REDACTED]
[REDACTED]
- 2) Staff-assessed conjunctival redness will be recorded a [REDACTED]
[REDACTED].

At approximately 95-minutes post-EEC entry (and after subject assessed itching and tearing and staff assessed conjunctival redness for all time-points post first dose have been completed), a second dose (one drop in each eye) of the same randomized treatment will be administered in each eye by the qualified site staff. Subject will continue to assess symptoms of ocular itching and tearing after the second dose [REDACTED]

[REDACTED], and staff-assessed conjunctival redness will be recorded at approximately post second dose [REDACTED]
[REDACTED].

Post-EEC exit (approximately t=215 minutes):

- 1) Subject assessed ocular itching and tearing will continue a [REDACTED]
[REDACTED]
- 2) Staff assessed conjunctival redness will continue to be recorded post-EEC exit [REDACTED]
[REDACTED]

Subjects will be asked to return in at least two weeks for Visit 4.

At Treatment EEC Session Two (Visit 4), all procedures performed at Visit 3 will be repeated except that each subject will be given a different treatment dependent on the treatment sequence the subject was randomized to [Reproxalap Ophthalmic Solution (0.25%) (Treatment A), Reproxalap Ophthalmic Solution (0.5%) (Treatment B), or Vehicle Ophthalmic Solution (Treatment C)].

At the end of the EEC session, subjects will be asked to return in at least two weeks (\pm 3 days) for Visit 5.

At Treatment EEC Session Three (Visit 5), all procedures performed at Visit 4 will be repeated except that each subject will be given a different treatment dependent on the treatment sequence the subject was randomized to [Reproxalap Ophthalmic Solution (0.25%) (Treatment A), Reproxalap Ophthalmic Solution (0.5%) (Treatment B), or Vehicle Ophthalmic Solution (Treatment C)]. At the end of the visit, a urine pregnancy test will be administered to WOCBP. Subjects will undergo ophthalmic examinations (Snellen VA, SLE, NCT, and a dilated fundus examination), clinical safety lab tests and vital signs will be collected to ensure safety prior to exit of the clinical trial.

3.2 Assigning Subjects to Treatment Groups

3.2.1 Subject Numbering

Each subject screened for the clinical trial will be assigned a unique subject number that will be used to identify the subject throughout subject participation in the clinical trial. If a subject fails to be randomized, the reason should be documented in the source documents and case report form (CRF). The subject will be considered a screen failure.

3.2.2 Randomization

Eligible subjects will be randomized 1:1:1 to one of three treatment sequences of ABC, BCA, CAB, where:

- Treatment A: Reproxalap Ophthalmic Solution (0.25%)
- Treatment B: Reproxalap Ophthalmic Solution (0.5%)
- Treatment C: Vehicle Ophthalmic Solution

Approximately 75 subjects (approximately 25 per treatment sequence) will be enrolled.

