pemphigoid, significant conjunctival scarring, chemical burn, herpetic or neurotrophic keratitis, Cryopyrin Associated Periodic Syndrome (CAPS), or keratoconus;

[REDACTED]

[REDACTED]

Statistical Analysis:

Approximately 150 subjects with ragweed-induced, moderate-to-severe allergic conjunctivitis will be screened in the EEC in order to randomize approximately 75 subjects, and for 60 subjects to complete the study. Approximately twenty-five (25) subjects will be assigned to each of three (3) treatment sequences, ABC, BCA, and CAB. While not based on formal power considerations, 60 subjects completed is sufficient to produce reasonably reliable statistical conclusions based on the following:

[REDACTED]

Prior to database lock, the Sponsor will finalize a statistical analysis plan (SAP) that will detail all planned analyses. Any analyses conducted in addition to those specified in the SAP will be clearly documented as post hoc.

In brief, the efficacy analyses of all efficacy endpoints will be carried out in the Intent-to-Treat (ITT) population. Supportive analyses may also be provided for Itching endpoint(s) using the Per-Protocol (PP) population.

Descriptive statistics of all activity endpoints as well individual data listings will be presented by treatment group and efficacy measures. For each efficacy endpoints, treatment comparisons will be made between Reproxalap Ophthalmic Solutions (0.25% and 0.5%) and vehicle. The treatment comparison will be performed using a mixed-effects Analysis of Covariance Model (ANCOVA) for a crossover study for 3 periods.

[REDACTED]

The endpoints that will be analyzed are the following:

AUC 0-212 mins for Itching on VAS scale
AUC 0-212 mins for Itching on 9 points scale
AUC 0-210 mins for Conjunctival Redness on 9 points scale
AUC 0-212 mins for Tearing on 4 points scale
AUC 0-212 mins for TOSS
AUC 0-92 mins for Itching on VAS scale
AUC 92-212 mins for Itching on VAS scale
AUC 0-32 mins for Itching assessed by VAS Scale
AUC 32-72 mins for Itching assessed by VAS Scale
All 0 time-point measurements will be pre-EEC entry/ baseline values. All the time-points are approximate values

Additional Exploratory Analyses

In addition, descriptive statistics including Change from Baseline (CFB) for each treatment and each post-EEC time-point may be derived and used as exploratory efficacy endpoints to evaluate the efficacy of Reproxalap Ophthalmic Solutions (0.25% and 0.5%). Other exploratory analyses may be added post-hoc.

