- Treatment B: Reproxalap Ophthalmic Solution (0.5%)
- Treatment C: Vehicle Ophthalmic Solution

	Sponsor: Aldeyra Therapeutics, Inc. Sponsor Protocol No. ALDNS2-203-D1
--	---

Approximately 75 subjects (approximately 25 per treatment sequence) will be enrolled with a target of 60 completers. As the actual discontinuation rate observed was lower than anticipated, the enrollment may be less than the planned 75 subjects.

Investigators, qualified site personnel, and subjects will be masked to the treatment sequence and investigational product (IP) administered in each treatment visits. The Sponsor will also be masked to the IP administered information until database lock.

EMERGENCY UNBLINDING

Emergency unmasking should only be performed when necessary to treat the subject. Most often, knowledge of the possible treatment assignments is sufficient to treat a clinical trial subject who presents with an emergency condition.

The investigator should make every effort to contact the Medical Monitor to discuss the subject's emergency and the need to unmask, prior to unmasking any subject. Please defer to the protocol for further details.

SUBJECT NUMBERING

Each subject screened for the clinical trial will be assigned a unique subject number that will be used to identify the subject throughout their participation in the clinical trial. If a subject fails to be randomized, the reason should be documented in the source documents and case report form (CRF). The subject will be considered a screen failure.

VII. EFFICACY ASSESSMENTS

[figure not shown]
[figure not shown]
At all EEC sessions (pre- and post-entry), assessments of ophthalmic evaluations by subjects and qualified site staff will be collected using an electronic Patient Data Acquisition Tablet™ (ePDAT™).

Refer to [**Table 2**](#) (Schedule of Staff-Assessed Conjunctival Redness Recording) [**Table 3**](#) (Schedule of Subject Assessed Itching and Tearing Table 3) for details on collection time points).

STAFF-ASSESSED SYMPTOM COLLECTION

At designated time points, qualified site staff will assess conjunctival redness in each subject using a standard 9-point (i.e., 0-4 scale with 0.5 unit increments).

Sponsor: Aldeyra Therapeutics, Inc.
Sponsor Protocol No. ALDNS2-203-D1

[figure not shown]

SUBJECT ASSESSED SYMPTOMS

At designated time points, subjects will be asked to report and rate symptoms associated with allergic conjunctivitis, including ocular itching and tearing.

Ocular Itching

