Data Collected Outside Study Schedule

Data collected at visits that occurred outside the time windows specified in the protocol will be included in the data listings but will not be included in the analyses.

Definition of Baseline

In general, baseline is defined as the last observed measurement prior to the first dose of study medication during Pre-EEC entry at visit (visit 3, visit 4 and visit 5). If patient has more than one non-missing measurement at different time point prior to the first dose, average of these assessment score will be taken to derive the baseline value. The baseline will be used in the change from baseline calculation for each treatment period.

	
Sponsor: Aldeyra Therapeutics, Inc. Sponsor Protocol No. ALDNS2-203-D1

--	---

Derived Variables

- Age is calculated in years after rounding down as follows:
Year of age = (Date [in days format] informed consent signed - Date [in days format] of birth) / 365.25.
- Efficacy assessments will be performed on both eyes. For conjunctival redness, assessments will be made in both temporal and nasal regions. For a symptom and at a specific EEC time point, from the multiple scores observed, the maximum score from both eyes and regions when applicable will represent the worst symptom score and thus will be used for the statistical analysis. This implies that all efficacy summary tables and treatments comparisons will use the maximum observed score at each ECC time points. The Listings of efficacy data however will provide all scores for the eyes and the regions as applicable.

The efficacy endpoints AUC will also be derived using the maximum score at each time point. Similarly, TOSS will be derived using the maximum score at each time point for the ocular itching, conjunctival redness and tearing symptoms.

- TOSS will be derived as the sum total of maximum score from ocular itching, conjunctival redness and tearing symptoms. However, the EEC time points for the ocular itching and tearing symptoms is different from the time points for the conjunctival redness. The scheduled time points for ocular itching will be used to represent the TOSS scheduled time points.

XII. STATISTICAL ANALYSES

MISSING DATA

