	
Sponsor: Aldeyra Therapeutics, Inc. Sponsor Protocol No. ALDNS2-203-D1

---	---

[figure not shown]
[figure not shown]
[figure not shown]
[figure not shown]
corresponding electronic CRF along with the reason the medication was taken.

Medications will be coded according to the WHO drug dictionary which includes the WHO Drug Preferred Name and the ATC Classification Level 2 and 4. Prior and concomitant medication data will be listed by subject.

STUDY DRUG ADMINISTRATION

The dosing dates, times during Treatment Visits 3 to 5 will be listed by subject and visit.

EFFICACY ANALYSES

Treatment Comparisons

Sponsor: Aldeyra Therapeutics, Inc.
Sponsor Protocol No. ALDNS2-203-D1

The following 3 contrasts will be evaluated for each primary endpoint:

- Reproxalap Ophthalmic Solution (0.50%) vs. Placebo
- Reproxalap Ophthalmic Solution (0.25%) vs. Placebo
- Reproxalap Ophthalmic Solution (0.50%) vs. Reproxalap Ophthalmic Solution (0.25%)

POST HOC ANALYSIS

1. Additional inferential analysis may be performed whereby additional covariates and other fixed factors may be used in models, depending on the significance of the term and the impact on contrast outcomes.
2. Responder analyses may be performed whereby treatment response may be defined as one and two-point improvements from mean and within-subject baseline and peak scores. In addition to GEE, time to event analyses may also be performed.

[REDACTED]	Sponsor: Aldeyra Therapeutics, Inc. Sponsor Protocol No. ALDNS2-203-D1
------------	---

[REDACTED]

[REDACTED]

[REDACTED]

[REDACTED]

[REDACTED]

SAFETY ANALYSES

All safety data will be analyzed using Safety population.

For safety analysis, summary descriptive statistics such as N, mean, SD, median, minimum and maximum will be provided by treatment group for continuous variables. Frequency distribution as number of subjects and percentage of subjects will be provided for categorical variables. No formal inferential tests will be performed on safety data.

Adverse Events/Adverse Drug Reactions

AEs will be coded using the Medical Dictionary for Regulatory Activities (MedDRA) coding dictionary [REDACTED] preferred term (PT) and system organ classification (SOC). Subjects will multiple events within the same SOC and/or PT are only counted once within the respective frequencies.

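### With three cyclic sequences each treatment has one fixed predecessor: unequal carryover would bias contrasts, and adjusting for it costs 3- to 5-fold variance, against about 1.2-fold with all six sequences

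*Protocol*

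**What the plan says.** Protocol 3.2.2 sets the allocation: "Eligible subjects will be randomized 1:1:1 to one of three treatment sequences of ABC, BCA, CAB, where" Treatment A is reproxalap 0.25%, B is 0.5% and C is vehicle. It adds: "Approximately 75 subjects (approximately 25 per treatment sequence) will be enrolled". The SAP repeats the same three sequences. No visible text explains why ACB, BAC and CBA are left out.

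The main visible protection against carryover is the interval between sessions, which are to be "separated by an approximate two-week washout period to ensure adequate elimination of responses caused by allergen exposure in the EEC" (Protocol 3.1) and to let mast cells recover. The interval is not worded consistently. The synopsis has two weeks with a 3-day window either way for Visits 4 and 5. Section 3.1 has a minimum of two weeks for Visit 4, and the same minimum with a 3-day window either way for Visit 5.

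The synopsis plans a "mixed-effects Analysis of Covariance Model (ANCOVA) for a crossover study for 3 periods"; the text after it is redacted, as are the SAP's General Considerations and parts of its Efficacy Analyses. The SAP evaluates three contrasts: each strength against vehicle, and 0.5% against 0.25%. It defines a pre-dose baseline at each treatment visit: "The baseline will be used in the change from baseline calculation for each treatment period".

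**The concern.** The three sequences form a single Latin square. Each treatment appears once in each period, but from the second session on it always follows the same other treatment. Treatment and predecessor are therefore largely confounded. If what remains from the previous session depends on which product was given, that remainder is read as part of the current treatment's effect.

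The dose contrast shows this most clearly. 0.5% always follows an active strength and 0.25% always follows vehicle. If both strengths leave some benefit behind and vehicle leaves none, 0.5% looks better than 0.25% even when the two are equal, which would be a false dose response. The usual answer is to fit carryover, but in this layout that is expensive. One stated objective is the feasibility of the chamber design itself, and whether repeated sessions are free of treatment-specific carryover belongs to that question.

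**Working it through.** **Inputs.** Sequences and 1:1:1 allocation: Protocol 3.2.2. Completers: 60 (Synopsis), taken as 20 per cyclic sequence, or 10 per sequence if six are used. Contrasts: SAP, Treatment Comparisons. Not in the documents: the size of any carryover (kept as a symbol) and the within-subject correlation r (shown from 0 to 0.7, plus fixed subject effects as the limit). The model has period, treatment and subject, with additive first-order carryover, equal sequence sizes, no dropout and no baseline covariate. The visible text gives no power, variance or effect figure to reproduce. Its allocation arithmetic agrees: 3 × 25 = 75.

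**Predecessors in ABC, BCA, CAB.** A follows C (in BCA and CAB), B follows A (in ABC and CAB), C follows B (in ABC and BCA).

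**Bias with no carryover term.** Let λ be the carryover benefit of a treatment on the next session's AUC. Subject and period effects cancel, so each treatment mean picks up its average carryover.
- Cyclic: one third of a treatment's observations are in the first period and two thirds follow its fixed predecessor. Bias(X−Y) = 2/3 × (λ of X's predecessor − λ of Y's predecessor).
- Six sequences: one third follow each of the other two treatments. Bias(X−Y) = 1/3 × (λ of Y − λ of X).

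Listed as 0.25%−vehicle / 0.5%−vehicle / 0.5%−0.25%; a negative sign means the benefit is understated:

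| Carryover pattern | Cyclic | Six sequences |
|---|---|---|
| Both strengths L, vehicle 0 | −0.67L / 0 / +0.67L | −0.33L / −0.33L / 0 |
| Only 0.5% carries L | −0.67L / −0.67L / 0 | 0 / −0.33L / −0.33L |
| 0.25% carries 0.5L, 0.5% carries L | −0.67L / −0.33L / +0.33L | −0.17L / −0.33L / −0.17L |
| Equal from all three | 0 / 0 / 0 | 0 / 0 / 0 |

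**Variance of a contrast, in units of residual variance.** Without carryover both designs give 2/N = 2/60 = 0.0333. Fitting carryover multiplies this by 1/(1 − R²), with R² = c²/(a × b). Per subject:
- a = 3, the treatment information.
- b = (2 + 3r)/(1 + 2r), the carryover information after allowing for subjects; it is 5/3 with fixed subjects.
- c = 2 in the cyclic design, where treatment and predecessor move together in both later periods; c = 1 with six sequences, where the two squares partly cancel.

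Substituting, the cyclic factor is (6 + 9r)/(2 + r) and the six-sequence factor is (6 + 9r)/(5 + 7r).

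| r | Cyclic factor | Cyclic variance | Six-sequence factor | Six-sequence variance |
|---|---|---|---|---|
| 0 | 6/2 = 3.00 | 0.100 | 6/5 = 1.20 | 0.0400 |
| 0.3 | 8.7/2.3 = 3.78 | 0.126 | 8.7/7.1 = 1.23 | 0.0408 |
| 0.5 | 10.5/2.5 = 4.20 | 0.140 | 10.5/8.5 = 1.24 | 0.0412 |
| 0.7 | 12.3/2.7 = 4.56 | 0.152 | 12.3/9.9 = 1.24 | 0.0414 |
| Fixed subjects | 1/(1 − 4/5) = 5.00 | 0.1667 | 1/(1 − 1/5) = 1.25 | 0.0417 |

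Generalised least squares on the full design matrices gives the same values. If a fixed sequence effect is also fitted, the cyclic factor is 5.00 at every r.

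**Equivalent completers after adjustment.** Cyclic: 60/5 = 12 to 60/3 = 20. Six sequences: 60/1.25 = 48 to 60/1.20 = 50.

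**Visit 3 alone, 20 per arm.** Variance 2/(20 × (1 − r)) = 0.10, 0.14, 0.20 and 0.33 at r = 0, 0.3, 0.5 and 0.7. This is never below the cyclic mixed model with carryover and without a sequence effect (0.10, 0.13, 0.14, 0.15).

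**The case against.** The strongest objection is that the harm is hypothetical. Only carryover that differs between treatments matters. It would have to survive about two weeks after two drops per eye, and nothing visible suggests that it does. Allergen priming common to all sessions causes no bias. The pre-dose baselines would show leftover symptoms, though not a changed response to the pollen. This stands, and it limits the weight of the point.

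Not every contrast is biased under every pattern. If both strengths carry over equally, the cyclic design leaves 0.5% versus vehicle clean, whereas six sequences without adjustment would shift it by −0.33L. This also stands: the gain comes from pairing six sequences with the adjustment.

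The 3- to 5-fold factor assumes a separate carryover for each treatment. If only active-versus-vehicle carryover is fitted, 0.5% versus vehicle loses nothing, and the other two contrasts rise 2.5-fold (r = 0) to 3.7-fold (r = 0.7), or 4.0-fold with fixed subjects. With a fixed sequence effect in the model, Visit 3 alone would be the more precise at low r (0.10 and 0.14 against 0.1667). Both are fair qualifications.

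The redacted text may already contain a carryover term. It may also be too late to change the sequences, since the SAP says: "As the actual discontinuation rate observed was lower than anticipated, the enrollment may be less than the planned 75 subjects". Finally, a single Latin square is a recognised design, the trial has no formal hypotheses, and the protocol synopsis names only comparisons with vehicle. These points lower the priority; they do not alter the design property. The SAP does add the dose contrast. Its only visible route for extra model terms is post hoc, chosen partly on significance and on the effect on the contrasts, which is a poor basis for a carryover term.

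**Conclusion.** The concern holds, as an inexpensive improvement worth considering. The fixed predecessors are a fact of the randomisation. Any bias is conditional on unequal carryover of unknown size, with a coefficient of 2/3 against 1/3 with six sequences. Six sequences do not remove unadjusted bias; they halve the largest coefficient and make adjustment affordable, with no loss of precision if carryover is never fitted. The figures rest on additive first-order carryover, equal sequence sizes, 60 completers without dropout, no baseline covariate, and an assumed range for r. The synopsis says "While not based on formal power considerations, 60 subjects completed is sufficient to produce reasonably reliable statistical conclusions"; under full carryover adjustment in the cyclic design, those 60 would carry the information of 12 to 20.

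**What to change.** **If randomisation has not begun.** Allocate the same approximately 75 subjects to ABC, BCA, CAB, ACB, BAC and CBA (75/6 = 12.5, so 12 or 13 each). Prespecify a first-order carryover model as a sensitivity analysis, unless the redacted text already has one. Cost: a new randomisation list and kit-sequence labels, and six sequences to manage instead of three. Subjects, visits and sessions are unchanged.

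**If it has begun.** Before unmasking, prespecify the carryover-adjusted mixed model as a sensitivity analysis, and state whether a fixed sequence effect is included. Keep a Visit 3-only comparison at most as a supporting check. Say in advance that the adjusted intervals will be wide, so a null carryover estimate would not exclude a meaningful one. Cost: one model and a short SAP addition. Six sequences then become advice for a later chamber trial.

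**In either case.** State in the SAP that the 0.5% versus 0.25% contrast assumes no unequal carryover; in the cyclic design this means that 0.25% and vehicle carry over equally. Reconcile the differing return-interval wording in the synopsis and Section 3.1, because the washout is the main visible safeguard.
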